- Discomfort from the blood pressure cuff: the pressure applied to the participant's arm will be lower than that typically applied during a blood pressure measurement. However, participant's may find this level of pressure to be uncomfortable. Participants will be asked after each trial their level of discomfort to assess whether they should or should not proceed with the study. Participants will also have the option to relay their discomfort to the study team through the MRI intercom system.
- Skin irritation: multiple rounds of data collection with the device could result in mild skin irritation. The cuff will be inflated less than five total times to minimize the likelihood the skin irritation is an issue.
- 3. Bruising from the device: pressure will be applied to the top of the device and transferred to the participant's arm. This could lead to slight bruising. The study team will work to continually gauge the participant's level of discomfort and will use longer breaks or stop the study if their discomfort is too great.

Arm 2: Methodology

In order to evaluate the specific aims above, the protocol and data collection templates described below have been developed. In Arm 2, the study team will thoroughly document the insertion of placebo using the SubQ Assist on 50 healthy adults.

Arm 2: Inclusion Criteria

1. Healthy adult subjects ages 18 to 49

2. Ability to understand study procedure and informed consent document

Arm 2: Exclusion Criteria

- 1. Patients with a history of keloid scarring
- 2. Pregnancy
- 3. Any rashes or skin conditions around the insertion site
- 4. Known silicone allergies
- 5. Known allergy to lidocaine
- 6. History of bleeding disorders or abnormal bleeding

Arm 2: Insertion Protocol

Below is the step-by-step procedure that will be used. The study will be conducted at Michigan Clinical Research Unit (MCRU) allowing us to take advantage of clinical services and supplies available.

- This trial will be conducted on a healthy adult population (50 participants) and a placebo will be used in place of the contraceptive implants. The implant will be made of FDA approved medical grade silicone with properties that match traditional contraceptive implants. The material grade is approved for implantation into the body for less than 24 hours and does not contain any pharmaceutical.
- 2. A trained physician study member will walk participants through the entire procedure.

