- 3. Participants who agree to participate will then be given the informed consent document to review with the physician. The physician will walk the participants through the document and provide the opportunity for the participant to ask any questions.
- 4. After signing the informed consent, a researcher will then collect background information on the participant including:
 - a. Height
 - b. Weight
 - c. Arm circumference
 - d. Age
- 5. Placebo implants will then be inserted by a trained physician using the SubQ Assist (See Appendix A for the insertion procedure). The device used in the trial will be 3D printed using biocompatible Class I resins. Each device will be sterilized using an autoclave prior to the procedure. Appendix B Provides more details with respect to the process of manufacturing and sterilizing the SubQ Assist. The placebo implants will be made by Albright Technologies (an ISO 13485 certified producer of medical devices).
- 6. The physician will use sterile gloves throughout the procedure. Iodine is used to disinfect the area where the SubQ Assist will come into contact with the participant and where the insertion will occur.
- 7. Lidocaine will be used as local anesthetic along the implant trajectory.
- 8. After administration the following measurements will be made:
 - a. Implant palpability: Can the implant be easily palpated through the skin and, if so, can the entire implant be palpated.

- b. Visibility: Can the implant impression be seen when the arm is in a relaxed position?
- c. Ultrasound measurement: Ultrasound images of the embedded implant will be taken (which will allow for post-processing to capture the depth of the individual implant).
 - i. A research assistant/co-investigator with expertise in ultrasound imaging will administer the ultrasound (Logiq V2 2016 by GE). A 10-15 MHz ultrasound with linear array and 50mm footprint will be used. The ultrasound will be set to superficial focus (<3cm).
 - 1. Two transverse images will be taken: at the distal and at the proximal ends of the implant.
 - 2. A third ultrasound image will be taken in the longitudinal direction.
- d. Bruising/Bleeding: Notes will be taken on whether any bruising/bleeding is occurring and, if so, how much. Sterile gauze will be used to assess the amount of blood loss (comparing pre- and post-procedure gauze weight to assess amount of blood loss).

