- 1. Participants will be called or emailed (depending on their preference) one week after the insertion procedure to assess any pain or discomfort associated with the insertion protocol.
- 2. The questions outline in Appendix C will be asked of all participants.
- 3. Any adverse events will be recorded

Arm 2: Follow-up Visit Protocol (3 weeks ± 1 week)

- 1. Participants will return for a follow-up visit three weeks after the insertion procedure (± 1 week).
- 2. During this visit, the incision will be checked for safe healing and infection. Photographs will again be taken of the insertion site to assess potential bruising. Photographs will not be identifiable (consist of upper arm only). Any adverse events will be recorded.

Arm 2: Placebo Implants

The placebo implants used in this study will be manufactured by Albright Technologies Inc (https://albrightsilicone.com). The placebo implant is made to the same specifications as the contraceptive implants with respect to both geometry and material characteristics. The implants are made from short-term implantable silicone which is a grade of silicone that can be implanted in the body for 29 days or less. Manufacturing will be done in a class ISO 7 compliant controlled environment room. Parts will be sterilized and packaged sterile allowing the research team to use a disposable sterile implants for each research participant.

Arm 2: Risks to Participants

The participants in this study will be healthy adults [18-49 years of age]. They will receive a placebo implant (using the SubQ Assist), additional measurements, implant removal, a follow-up check-in, and a follow-up visit.

Participants in this study will be receiving placebo implants. There is no anticipated risk of a decrease in cognitive function during the study and participants will be allowed to withdraw from the study at any time. There is a highly unlikely risk of a reaction to the lidocaine local anesthetic that could occur. A strong reaction would result in the participant being prematurely withdrawn from the study. To minimize this risk, participants will be asked about any prior reactions to anesthesia they may have had in the past during recruitment. Placebo implants will be made of implantable grade silicon (See Appendix D). We will therefore ask participants about potential silicone allergies prior to enrollment in the study. Study

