Appendix A

[figure not shown]
Below we have a detailed discussion of how the SubQ Assist Implant Insertion Device is used to insert the placebo implants:

- 1. A sterile drape is first draped underneath the upper arm of the participant and a sterile field is created.
- 2. An insertion mark is made at 6-8cm above the epicondyle.
- 3. Iodine is used to disinfect the area where the SubQ Assist will come into contact with the participant and where the insertion will occur.
- 4. The SubQ Assist is removed from its sterile packaging and clipped onto the blood pressure cuff (Step 1 below).
- 5. The blood pressure cuff is wrapped around the participant's upper arm aligning the device with the insertion site mark (Step 2 below).
- 6. Once secured, the blood pressure cuff is inflated to ~40mm Hg (Step 3 below). This pushes the skin and subcutaneous tissue into the cavity on the underside of the SubQ Assist.
- 7. The lidocaine is then inserted through the guide on the front of the device; placing the local anesthetic along the implant trajectory.
- 8. The cuff is deflated while the lidocaine takes effect.
- 9. The cuff is re-inflated after a two minute waiting period to ~40mm Hg.
- 10. The implant trocar is removed from its sterile packaging and inserted through the guide of the SubQ Assist (Step 4 below).
- 11. The plunger is removed and the sterile placebo implant is removed from its packaging and inserted into the trocar. The plunger is inserted until resistance is felt, the trocar is then pulled back until it touches the plunger.
- 12. The trocar is rotated to insert an implant in the second directions.
- 13. The trocar is removed completely, the cuff is deflated and removed from the patients arm.
- 14. The insertion site is cleaned and a steristrip is applied.

Step 4

Step 5

Step 6

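### Arm 2 neither excludes nor asks about a contraceptive implant currently in the arm to be used, and neither fixes nor records which arm that is

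*Protocol*

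**What the plan says.** Arm 2: Inclusion Criteria has two items: "Healthy adult subjects ages 18 to 49", and the ability to understand the procedure and the consent document. Sex is not restricted, and the exclusion of pregnancy shows that women are expected.

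Arm 2: Exclusion Criteria has six items. Three could bear on the state of the arm or on the incision: "Patients with a history of keloid scarring", "Any rashes or skin conditions around the insertion site" and "History of bleeding disorders or abnormal bleeding". The other three are pregnancy, silicone allergy and lidocaine allergy.

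Step 4 of Arm 2: Insertion Protocol lists height, weight, arm circumference and age as background data. Arm 2: Risks to Participants adds questions about silicone allergy and earlier reactions to anesthesia.

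On the site, Appendix A says "An insertion mark is made at 6-8cm above the epicondyle" and has the cuff and device put on the upper arm. It does not say left or right. On the rod, Arm 2: Placebo Implants says "The placebo implant is made to the same specifications as the contraceptive implants with respect to both geometry and material characteristics".

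Placement is assessed after insertion only. Step 8 asks "Can the implant be easily palpated through the skin", then whether the implant can be seen, and then takes ultrasound images. Arm 2: Data Analysis names the ultrasound depths and angle as the key data.

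**The concern.** Taken together, these provisions allow a matching rod and a guided trocar to go into an arm that already holds a contraceptive implant. The Background says such implants protect for three to five years, so current users fall within the age range of the trial.

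Two things are at stake.

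- **Safety.** The trocar could strike or displace the existing implant, or the removal step could disturb it. Safety is a stated objective, and the Arm 2 risk section does not mention this possibility.
- **Attribution.** Palpability and visibility are yes/no readings with no reading before insertion to compare against. A neighbouring rod that can be felt or seen would most naturally turn a no into a yes, which flatters the device. Ultrasound images could also be affected, though that is less likely.

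This belongs in the protocol. Eligibility and the choice of arm are settled before any analysis, so a statistical analysis plan could not close the gap.

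**Working it through.** **Step 1: does any provision close the gap?**

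| Place in the protocol | What it covers | Implant already in the arm? |
|---|---|---|
| Arm 2 inclusion (2 items) | Health and age; understanding | No |
| Arm 2 exclusion (6 items) | Keloid, pregnancy, skin at the site, silicone, lidocaine, bleeding | No; a rod under intact skin is not a rash or skin condition |
| Insertion protocol, step 4 | Height, weight, arm circumference, age | No |
| Arm 2 risks | Silicone allergy, reactions to anesthesia | No |
| Appendix A, steps 1 to 6 | Drape, mark, disinfect, fit device, inflate | No check before insertion; side not named |
| Insertion protocol, step 8 | Palpability, visibility, ultrasound | After insertion only |

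By contrast, Arm 1, which inserts nothing, pre-screens participants for metal inside the body and names implanted devices as a hazard of the scan.

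**Step 2: do the sites overlap?** The Background places contraceptive implants under the skin on the underside of the arm. Appendix A puts the study device on the upper arm, 6 to 8 cm above the epicondyle. Overlap is a reasonable inference. The protocol does not state it.

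**Step 3: how likely is it that a carrier is enrolled?** The protocol gives n = 50 for Arm 2 and no proportion of carriers. Let p be the assumed proportion of enrolled adults with a current implant in the arm used. The expected number is 50p, and the chance of at least one is 1 − (1 − p)^50.

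| Assumed p | Expected number | Chance of at least one |
|---|---|---|
| 0.5% | 0.25 | 22% |
| 1% | 0.5 | 39% |
| 2% | 1.0 | 64% |
| 5% | 2.5 | 92% |
| 10% | 5.0 | 99.5% |

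These are chances of enrolling a carrier. They do not measure bias.

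**Step 4: what would an affected reading do to the results?** Each participant has weight 1/50 = 2%. One wrong palpability or visibility answer moves the proportion by 2 percentage points. If k depths are each wrong by d mm in the same direction, the mean moves by k × d / 50:

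| k | d = 1 mm | d = 2 mm | d = 5 mm |
|---|---|---|---|
| 1 | 0.02 mm | 0.04 mm | 0.10 mm |
| 2 | 0.04 mm | 0.08 mm | 0.20 mm |
| 5 | 0.10 mm | 0.20 mm | 0.50 mm |

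The values of d are assumptions. The last row requires five carriers, all misread in the same direction, and is an extreme case. The protocol gives no standard deviation or numerical depth limit against which to judge these shifts. What can be said is that one misread participant passes on only 2% of the reading error to the mean.

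**The case against.** The strongest reply is that the procedure itself guards against confusion. The physician marks the site and guides the trocar there. An operator with ultrasound expertise images both ends of the rod and its length. The rod comes out through the same incision at the same visit, and it is measured and photographed. A woman who carries an implant would normally know it, and could say so when a physician explains what will be inserted and where.

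Much of this stands. A reader might infer that the depth data may come from another implant and so say nothing reliable about the device. The documents do not support that: recording the wrong rod would mean overlooking a fresh insertion track. Some residual risk remains, because depth is obtained by later processing of the images and the person scanning need not be the person who inserted. Appendix A also turns the trocar to place an implant in a second direction, so an additional rod need not look out of place.

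A reader might also extend the point to past implants, through scar tissue that steers the trocar or tethers the skin. No section describes such a mechanism, and an implant that has been removed cannot be felt, seen or imaged. That extension is not supported.

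The reply does not remove the gap. A participant's chance remark is not a written safeguard. The safety issue does not depend on anyone misreading an image, although it does require that the existing implant goes unnoticed, and the protocol neither describes nor quantifies it.

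**Conclusion.** The point holds for an implant currently in the arm to be used. Followed as written, Arm 2 can enrol a carrier, and no section asks about an implant, checks for one, or fixes or records the side.

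The likely effect on the trial's summary results is small: 2 percentage points in a proportion per wrong answer, and 0.02 to 0.10 mm in the mean depth per wrong reading, given assumed errors of 1 to 5 mm. A reader might take chances such as 92% or 99.5% as the size of the problem. They rest on assumed proportions of carriers and give only the chance that at least one is enrolled.

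The case for change therefore rests on participant safety and on being able to attribute each palpability, visibility and ultrasound reading to the study rod. It does not rest on material bias in the mean depth. It is a cheap improvement to the protocol, and no stated figure is in error.

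**What to change.** Add to Arm 2: Exclusion Criteria: *Current subdermal implant in the upper arm to be used for the study.*

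In step 4 of Arm 2: Insertion Protocol, ask about present implants and record which arm is used. A past implant may be recorded as a descriptive item but need not exclude.

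The cost is one exclusion line and two data items by amendment, with no added procedure. A few volunteers would use the other arm or would not be enrolled.

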- e. Photograph: A close-up photo (using Sony DSC-RX100) of the insertion sight will be taken to document the insertion and the insertion site. This will also be used to assess bruising. The photograph will not be identifiable (upper arm only).
- f. A case report will be created by the physician to assess the ease of use of the SubQ Assist and to make note of any issues with insertion. The physician administering the implant will address the following in the report:
 - i. Did you encounter any issues with the following steps in the insertion process?
 - 1. Clipping the SubQ Assist onto the blood pressure cuff and wrapping it around the patients' arm?
 - 2. Inflating the cuff to the appropriate pressure?
 - 3. Administering the lidocaine?
 - 4. Inserting the trocar?
 - 5. Inserting the implant?
 - 6. Removing the SubQ Assist?
- 9. Once all measurements are completed, the physician will remove the placebo implant through the original incision made by the implant trocar used. Removing implants through this incision will minimize scarring for the participant. In some cases, a slightly large incision will be required in order to remove the implant (up to 3mm in length) and will be made via a scalpel.
 - a. More anesthetic may be applied if necessary during removal based on the following scenarios:
 - i. Original dose of lidocaine wears off
 - ii. Original dose of lidocaine was too small for removal
 - iii. Implant removal is complicated and requires larger inceision
- 10. After removal, the implants will be measured and photographed (participant not in photograph) to ensure the implant removal was complete.
- 11. When implant removal is confirmed, a steristrip will be used to protect the incision from infection and facilitate healing.
- 12. Participants will be given an instructions on how to care for the incision and check for infection issues. The following points will be explained to participants:

- a. Only touch the steristrip with clean, washed hands.
- b. Keep the steristrip on for 3 days (until the wound has healed over) to prevent dirt and bacteria from reach incision.
- c. Keep the incision site dry.
- d. Contact the research team or your doctor if you see any of the following signs of infection: redness, oozing, bleeding, inflamed, increasing pain/itchiness, other signs of discomfort in the area of your incision.

Arm 2: Follow-up Check-in (7 days)

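### Do the two different implantation limits given for the placebo silicone leave the trial without a safety limit for a rod that cannot be removed the same day?

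*Protocol*

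**What the plan says.** Arm 2 places a silicone placebo rod in each of 50 healthy adults. The protocol gives the permitted time in the body twice.

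- Arm 2: Insertion Protocol, step 1: "The material grade is approved for implantation into the body for less than 24 hours and does not contain any pharmaceutical".
- Arm 2: Placebo Implants: the rods are short-term implantable silicone, "a grade of silicone that can be implanted in the body for 29 days or less".

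Both statements concern the same product. Step 5 of the Insertion Protocol says "The placebo implants will be made by Albright Technologies", and the Placebo Implants section says "The placebo implants used in this study will be manufactured by Albright Technologies Inc". Nothing points to a second product or grade.

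On how long the rod stays in, step 9 says: "Once all measurements are completed, the physician will remove the placebo implant through the original incision made by the implant trocar used". The same step lists the situations in which more anesthetic may be given, one being "Implant removal is complicated and requires larger inceision". Step 10 adds a check: "After removal, the implants will be measured and photographed (participant not in photograph) to ensure the implant removal was complete". In step 11 the site is dressed once removal has been confirmed.

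**The concern.** Two operative sections state incompatible maximum durations for one investigational material, and neither refers to the other. The protocol's Background describes implants placed too deep and hard to remove as the problem the device is meant to solve, and steps 9 and 10 show that difficult or incomplete removal was in mind. If a rod or fragment did stay in, a reader could not tell from the protocol whether it was past its material limit the next morning or still within it at the 3-week visit. The participants are healthy volunteers with nothing to gain from the rod, and safety is a stated objective. If the limit governed how such an event was classified or followed, the conflict could affect the safety results.

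**Working it through.** No sample size, power or error rate is involved. The check sets the two limits against the protocol's own time points and rules.

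**1. Size of the conflict.** Limit A (Insertion Protocol, step 1) is less than 24 hours. Limit B (Placebo Implants) is 29 days or less: 29 × 24 = 696 hours. The ratio is 696 / 24 = 29. The first statement says approved and the second says only that the grade can be implanted for that time, but each is a ceiling, so the difference in wording does not remove the conflict.

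**2. Time points.** The follow-up visit is at 3 weeks ± 1 week: 21 − 7 = day 14 to 21 + 7 = day 28.

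| Situation | Limit A (< 24 h) | Limit B (≤ 29 days) |
|---|---|---|
| Removal in the insertion session (steps 9–11) | met | met |
| Piece still in place after 24 hours | exceeded | met |
| Piece found at the visit, day 14–28 | exceeded | met |

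Only the first row is planned. The other two arise only if removal fails.

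**3. Does any rule use the limit?**

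- Steps 9 to 11 of the Insertion Protocol: removal follows the measurements and is then verified. No duration enters.
- Arm 2: Data Analysis: distal depth, proximal depth, angle and average depth, all from ultrasound images taken before removal. No duration enters.
- Adverse Events: all adverse events and complications go on the case report forms. For each adverse effect, enough information is sought to judge seriousness and the causal link to the device or other study treatment. Effects felt to be associated are followed until they resolve or stabilise. No duration enters.

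A rod or fragment that could not be removed would be a complication on the day of insertion under either limit, and would be recorded that day.

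**4. Would a rule built on the limit help?** Suppose a piece left beyond the limit had to be recorded as device-related. Under limit B the rule would apply only after day 29. The last possible visit is day 28, and adverse events are recorded only until the final visit, so the rule would never operate. Under either limit it would fix causality in advance, where the Adverse Events section asks for an assessment of each effect.

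**5. What 50 participants can exclude.** With 0 retained rods in 50, the exact upper limits are 1 − 0.05^(1/50) = 5.8% (one-sided 95%) and 1 − 0.025^(1/50) = 7.1% (two-sided 95%). These hold whichever duration is printed, so they say nothing about what the conflict costs.

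**The case for a change.** The strongest case for acting is that this is a factual contradiction about a material put into healthy volunteers, that failed removal is foreseeable, and that checking the supplier's certificate costs almost nothing. Step 9 provides for more anesthetic and a scalpel incision of up to 3 mm, whereas the Background says deeply embedded implants can need imaging and surgery. Appendix A, step 12, mentions inserting an implant in a second direction, so a participant may carry more than one rod. The Arm 2 risk section does not mention a retained rod. Someone judging causality might also want one agreed material limit to refer to.

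The contradiction itself stands in full. It cannot be explained away by noting that material usable for 29 days is also usable for one, because step 1 states a ceiling on the grade and not a planned time in place.

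The rest has less force. The protocol gives no path for a removal that cannot be confirmed, but that would be equally true if both sections printed the same limit; it is a separate matter. The Background's account of deep placement concerns free-hand insertion, whereas here a trained physician uses the guide. An assessor who wants the material limit would have to take it from the supplier's documentation, and the assessment is required either way. The risk section refers to an Appendix D for the silicone, which is not in the text at hand. It may hold the specification, though it could not make the two printed limits agree.

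**Conclusion.** The limit is not undefined: it is stated twice and inconsistently, by a factor of 29. This is a clerical inconsistency with no effect on any endpoint, analysis, recording rule or participant treated as planned. A participant whose removal failed would be recorded, assessed and, if the effect was felt to be associated with study products, followed in the same way under either limit. The two sentences must be reconciled with the supplier's documentation, and no view is taken here on which is right, but doing so alters nothing the trial does or concludes. A reporting rule tied to the limit would bring no gain, and under the longer limit it could never apply.

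This rests on two assumptions: that removal takes place in the insertion session as steps 9 to 11 describe (no hours are given), and that an implant or fragment that cannot be removed is treated as a complication under the Adverse Events section, which is its ordinary reading.

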Development of the SubQ Assist Implant Insertion Device would dramatically reduce the training barriers to accessing long-acting contraceptive implants. It would enable Ministries of Health in low- and middle-income countries to enable their community healthcare workers (who are readily accessible in rural areas) to administer these implants safely and effectively. This would open up a long-acting contraceptive option to a population of women who are currently underserved and have little access to modern contraception. Based on our analysis of United Nations Data on contraceptive implant use, we estimate that implementation of the SubQ Assist Implant Insertion Device in Ethiopia, Ghana, Kenya, and Uganda would lead to ~750,000 women receiving implants in underserved, rural areas (that currently have limited access. The study below will form the basis for clinical data needed to prove the safety and efficacy of the device.

Research Study

To date, we have performed simulator testing and cadaver testing to assess the efficacy of the SubQ Assist Implant Insertion Device. A trial to assess the safety and efficacy in human subjects is now needed to fully understand how effective the SubQ Assist is with respect to administering contraceptive implants. The study proposed below will allow us to understand whether the SubQ Assist is safe and can effectively place implants just under the skin in the subcutaneous layer.

Objective

The objective of this study is assess the safety and efficacy of the SubQ Assist device.

Specific Aims

SP1: Assess how soft tissue physically behaves when pressurized by the SubQ Assist Implant Insertion Device via a blood pressure cuff.

SP2: Determine the efficacy of the SubQ Assist Implant Insertion Device by measuring the depth of a placebo implant via ultrasound.

SP3: Identify any side effects associated with use of the SubQ Assist as compared to those associated with traditional standard insertion.

Arm 1: Methodology

One factor that may negatively affect the accuracy of the SubQ Assist Implant Insertion Device is the compression of the soft tissue and skin when the blood pressure cuff is inflated around the upper arm. To investigate this, we will be taking Magnetic Resonance Images of the SubQ Assist device inflated around the arm of participants in this arm of the study.

Arm 1: Inclusion Criteria

- 1. Healthy adults ages 18 to 49
- 2. Ability to understand study procedure and informed consent document

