Appendix C

Arm 2: Follow-up phone call / questionnaire:

- 1. On a scale of 1 to 10, what pain do you currently feel in your upper arm?
- 2. Is there any bruising on your upper arm?
- 3. Has there been any fluid draining from the incision?
- 4. Has there been any redness or swelling of the insertion site?
- 5. Has there been any bleeding from the insertion site?

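### Arm 2 bruising: photographs fall on the insertion day before removal and at days 14 to 28, and the day-7 question covers current bruising only, so short-lived bruises are likely to be under-counted

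*Protocol*

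**What the plan says.** Arm 2 is a single group: "the study team will thoroughly document the insertion of placebo using the SubQ Assist on 50 healthy adults". Its safety data serve SP3: "Identify any side effects associated with use of the SubQ Assist as compared to those associated with traditional standard insertion". Bruising is scheduled for assessment at three times.

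- **Insertion session.** Arm 2: Insertion Protocol, step 8d: "Notes will be taken on whether any bruising/bleeding is occurring and, if so, how much". Step 8e adds a close-up photograph of the insertion site, of which the protocol says "This will also be used to assess bruising". Step 9 comes next: "Once all measurements are completed, the physician will remove the placebo implant through the original incision made by the implant trocar used". Step 10 photographs the removed implant, not the arm.
- **Day 7.** A call or email puts the Appendix C questions to every participant. Question 2 reads "Is there any bruising on your upper arm". Questions 3 to 5 (drainage, redness or swelling, bleeding) ask whether there has been any. Adverse events are also recorded.
- **Follow-up visit, 3 weeks ± 1 week.** "Photographs will again be taken of the insertion site to assess potential bruising". Adverse events are recorded here too.

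The Adverse Events section has events recorded from consent to the last visit, whether seen by the investigator or reported by the participant. Each needs a description, the date it was first observed, any action taken and the outcome.

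**The concern.** The protocol means to use bruising as a safety measure. It collects a note, two sets of photographs and a questionnaire item for it. Read together, these leave a gap from the end of the session-day measurements to the day-7 contact, and the item that could look back over the gap is worded so that it does not.

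Two kinds of bruise can fall into the gap: one from insertion that was not yet visible at steps 8d and 8e, and one from removal. The second cannot appear in the session note or photograph at all, because both come before step 9, which in some cases needs a small scalpel incision.

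Any loss goes one way, since a missed bruise lowers the count and nothing in the schedule raises it. Arm 2 has no standard-insertion group, so the SP3 comparison has to use outside figures. If those captured bruising more completely, the shortfall would look like an advantage of the device.

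**Working it through.** The protocol states no bruise rate, duration or detection figure, so there is nothing to reproduce. The check has two parts.

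**1. Coverage by time, from the text**

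| Period | Scheduled bruising item | What it captures |
|---|---|---|
| Day 0, after insertion, before removal | Steps 8d and 8e | Bruising visible then |
| Day 0 after removal, up to day 7 | None | Nothing |
| Day 7 | Appendix C question 2 | Bruising present that day, yes or no |
| Days 14 to 28 (21 ± 7) | Photograph | Bruising still visible then |

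A bruise that appears after step 8e and is gone by day 7 meets no scheduled bruising item. A bruise present at day 7 but gone by the visit is a yes answer with no image, and Appendix C does not ask its size or dates. If question 2 had the form of questions 3 to 5, it would in principle cover every bruise noticed from the procedure to day 7, subject to recall.

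**2. How much could be lost (illustrative)**

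Assumptions, none of them from the protocol: time from the procedure to resolution is log-normal with log-SD 0.4 and median m between 4 and 14 days, and the follow-up visit falls uniformly over days 14 to 28.

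Share still present at day t: S(t) = 1 − Φ( ln(t/m) / 0.4 ).

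Example, m = 10, t = 7: ln(0.7) = −0.357; −0.357/0.4 = −0.892; S(7) = 0.81.

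Example, m = 4, t = 7: ln(1.75) = 0.560; 0.560/0.4 = 1.40; S(7) = 0.08.

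The share present at the visit is S(t) averaged over t from 14 to 28, found by simulation with 400,000 draws.

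| Assumed median (days) | Present at day 7 | Present at follow-up photograph |
|---|---|---|
| 4 | 8% | about 0% |
| 5 | 20% | 0.1% |
| 7 | 50% | 0.8% |
| 10 | 81% | 5% |
| 14 | 96% | 20% |

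The share gone by day 7 is the complement: 100 − 8 = 92% at a median of 4 days, and 100 − 96 = 4% at 14 days. That is a ceiling on what the schedule loses. Bruises already noted at step 8d are not lost, and bruises volunteered as adverse events are recovered.

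The two columns behave differently. The follow-up photograph finds a minority of bruises over the whole range. The day-7 loss runs from almost all to almost none.

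**The case against.** The strongest reply is that adverse events are recorded throughout, from participant report as well as observation, with a date and an outcome, and are recorded again at day 7 and at the visit. A bruise that has cleared can therefore still enter the data. Step 8d also asks how much bruising there is, so extent is not ignored altogether. An extensive bruise is the kind least likely to be both gone and unmentioned at day 7. Finally, the protocol's key data are the ultrasound depths, and bruising is descriptive.

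Most of this stands, and it limits the point to short-lived bruises and to likely, not certain, under-counting. It does not close the gap. No scheduled question asks about past bruising, and the list of signs that participants are told to report (step 12d) does not name bruising. A small, painless bruise that has faded depends on someone choosing to mention it.

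A reader might infer more than the documents support:

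- **That iodine staining spoils the session photograph.** Step 6 says "Iodine is used to disinfect the area where the SubQ Assist will come into contact with the participant", but Appendix A step 14 cleans the insertion site at the end of insertion, and step 8e is a close-up of that site. Residual staining in the frame is not established.
- **That the schedule misses bruising altogether.** It does not: the day-7 question catches every bruise still present and reported that day.
- **That bruising is the most expected side effect.** The protocol does not say so. It describes bruising from the device only under the Arm 1 risks, as slight, in a list headed as rare to infrequent. Arm 1 also allows cuff pressures up to 100 mm Hg, against about 40 mm Hg in Arm 2.

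**Conclusion.** The point holds in a limited form. From the text alone: both sets of photographs are poorly placed to measure how often bruising occurs, the session assessments cannot show bruising from removal, and question 2 is the only one of the four yes/no items in Appendix C restricted to the day of contact. Bruises that appear after the session and clear before day 7 rest on unprompted reporting and are likely to be under-counted.

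The size cannot be fixed from the protocol. The 8% to 96% at day 7 and the 0% to 20% at follow-up rest wholly on the assumed log-normal form, its spread, the range of medians and uniform visit timing. They support a firm statement about the late photograph and only a wide range for the day-7 item. No number of missed bruises among the 50 participants can be given, because that would also need a bruise rate, which the protocol does not state.

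The direction is clearer: the count can only be too low. Whether this favours the device under SP3 depends on the outside figures not sharing the same loss. The point is worth acting on because the remedy is nearly free, not because a large bias has been shown.

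**What to change.** 1. Reword Appendix C question 2 to: *Since the procedure, has there been any bruising on your upper arm? If so, how large was it at its largest, when did it appear, and when did it go?* This matches the look-back form of questions 3 to 5.
2. Report the photograph at 3 weeks ± 1 week as showing residual marks and healing, not the incidence of bruising.
3. Optionally, invite participants who report bruising at day 7 to email a photograph of the upper arm.

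**Cost.** Items 1 and 2 change one question and one line of reporting, with no added visit, staff or procedure. The look-back answer carries some recall error over a week. The optional photographs will vary in quality and some will be missing, so they should support the answer to question 2, not replace it.
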